9.2 Serious Adverse Events

9.2.1 Definition

A serious adverse event (SAE) is any adverse event (experience) that in the opinion of either the investigator or sponsor results in **ANY** of the following:

- Death.
- A life-threatening adverse event (experience). Any AE that places a patient or patient, in the view of the Investigator or sponsor, at immediate risk of death from the reaction as it occurred. It does **NOT** include an AE that, had it occurred in a more severe form, might have caused death.
- Inpatient hospitalization or prolongation of existing hospitalization (for > 24 hours).
- A persistent or significant incapacity or substantial disruption of the ability to conduct normal life functions.
- A congenital anomaly or birth defect.
- Important Medical Event (IME) that, based upon medical judgment, may jeopardize the patient and may require medical or surgical intervention to prevent one of the outcomes listed above.

9.2.2 Reporting Serious Adverse Events

All new SAEs occurring from the date the patient signs the study consent until 30 days after the last intervention or a new treatment is started, whichever comes first, will be reported. The RPCI SAE Source Form is to be completed with all available information, including a brief narrative describing the SAE and any other relevant information.

SAEs occurring after the 30 day follow up period that the investigator determines to be possibly, probably or definitely related to the study intervention should be reported.

SAEs identified as an Unanticipated Problem by the Investigator must be reported. Please refer to [Section 9.5.2](#) for details on reporting Unanticipated Problems.

9.3.1 E-Mail: [contact] Follow-Up for Serious Adverse Events

All related SAEs should be followed to their resolution, until the study patient is lost to follow-up, the start of a new treatment, or until the study investigator assesses the event(s) as stable or irreversible. New information will be reported when it is received.

9.4 Unanticipated Problems

9.4.1 Definition

An Unanticipated Problem (UP) is any incident, experience, or outcome that meets all of the following criteria:

- Unexpected (in terms of nature, severity, or frequency) given:
 - The research procedures that are described in the study-related documents, including study deviations, as well as issues related to compromise of subject privacy or confidentiality of data.
 - The characteristics of the patient population being studied.

- Related or possibly related to participation in the research (possibly related means there is a reasonable possibility that the incident, experience, or outcome may have been caused by the procedures involved in the research).
- Suggests that the research places subjects or others at a greater risk of harm (including physical, psychological, economic, or social harm) than was previously known or recognized and if in relation to an AE is also deemed **Serious** per **Section 9.2**.

9.4.2 Reporting Unanticipated Problems

Unanticipated problem reporting will begin at the time of participant consent. The Unanticipated Problem Form will be submitted to the CRS Compliance Office within 1 business day of becoming aware of the Unanticipated Problem.

When becoming aware of new information about an Unanticipated Problem, submit the updated information to CRS Compliance with an updated Unanticipated Problem Form. The site Investigator or designated research personnel will report all unanticipated problems, whether related or unrelated to the investigational agent(s) to the **IRB in accordance with their local institutional guidelines**.

Network sites please see **Appendix A** for reporting instructions.

9.5 FDA Reporting

When RPCI is the IND holder the following describes the FDA reporting requirements by timeline for AEs and new safety findings that meet the criteria outlined below:

Within 7 Calendar Days

Any adverse event that meets **ALL** the following criteria:

- Related or possibly related to the use of the study drug;
- Unexpected; and
- Fatal or life-threatening.

Within 15 Calendar Days

Any adverse event that meets **ALL** the following criteria:

- Related or possibly related to the use of the study drug;
- Unexpected; and
- Serious but not fatal or life-threatening.

Or, meets **ANY** of the following criteria:

- A previous adverse event that is not initially deemed reportable but is later found to fit the criteria for reporting (report within 15 days from when event was deemed reportable).
- Any findings from other studies, including epidemiological studies, pooled analysis of multiple studies, or other clinical studies conducted with the study drug that suggest a significant risk in humans exposed to the drug.
- Any findings from animal or in vitro testing that suggest a significant risk for human patients including reports of mutagenicity, teratogenicity, or carcinogenicity or reports of significant organ toxicity at or near the expected human exposure.
- Any clinically important increase in the rate of occurrence of a serious, related or possibly related adverse event over that listed in the protocol or investigator brochure.

Sponsors are also required to identify in IND safety reports, all previous reports concerning similar adverse events and to analyze the significance of the current event in the light of the previous reports.

Reporting Process

The principal investigator or designee will complete and submit a FDA Form 3500A Medwatch for any event that meets the above criteria. Forms will be submitted to the CRS Compliance Office email to: [contact].

10 DATA AND SAFETY MONITORING

This study will be reviewed at the scheduled RPCI data and safety monitoring committee meetings and the minutes are forwarded to the IRB for review.

11 STATISTICAL METHODOLOGY

11.1 Sample Size Determination and Analysis

In a Phase II and Phase III study of single agent topotecan or single agent irinotecan as shown in **Table 1** in recurrent SCLC, the median time to progression of the arms were 2.2 - 4 months.^{6,8-12} Based on this, the primary endpoint of this trial will be the proportion of patients who are progression-free at 18 weeks. Progression-free survival was chosen as the primary endpoint, rather than response rate, as this is appropriate clinical endpoint for cytotoxic agents such as NKTR-102 and for SCLC. A single-stage design will be used to assess the primary endpoint for each patient group. A treatment success was defined as a patient who was progression-free at 18 weeks. To evaluate Group A, the largest success proportion where the proposed treatment regimen would be considered ineffective in this population is 5%, and the smallest that would warrant further subsequent studies is 25%. Twenty evaluable patients will be entered on this study. If 2 or fewer successes are observed, this regimen will be considered ineffective in this patient population. If 3 or more successes are observed, this will be considered evidence that this treatment may be recommended for further testing in subsequent studies. Assuming that the

number of successes is binomially distributed, this design controls the Type I Error to be $< 10\%$ and has 90% power to detect 25% 18-week PFS rate. To evaluate Group B, the largest success proportion where the proposed treatment regimen would be considered ineffective in this population is 10%, and the smallest that would warrant further subsequent studies is 35%. Eighteen evaluable patients will be entered on this study. If 3 or fewer successes are observed, this regimen will be considered ineffective in this patient population. If 4 or more successes are observed, this will be considered evidence that this treatment may be recommended for further testing in subsequent studies. Assuming that the number of successes is binomially distributed, this design controls the Type I Error to be $< 10\%$ and has 90% power to detect 25% 18-week PFS rate. Patients who come off study (e.g., due to toxicity) and start an off-protocol therapy prior to 18 weeks will be considered failures at that point.

The evaluable population is defined as patients who meet eligibility requirements and receive any protocol treatment. Unevaluable patients will be replaced.

Progression-free survival is defined as the time from registration to the date of first documented disease progression or death. Survival time is defined as the time from registration to death due to any cause. Patients who loss-to-follow-up or alive at time of analysis will be censored at the last contact of known alive. The distribution of time to disease progression and survival time will be estimated in each group using the method of Kaplan–Meier. Probability of PFS at 18 weeks and 24 week and probability of survival at 3, 6, and 9 months will be estimated. All eligible and treated patients will be included in the analysis of the primary endpoint.

All adverse events, regardless of attribution, will be summarized (overall and by group).³⁴

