1.5 Risks Associated with NKTR-102

A majority of NKTR-102 related treatment-emergent adverse events (TEAEs) occurred in the system organ class (SOC) of GI disorders with diarrhea experienced most commonly by 85.5% of patients, followed closely by nausea (77.6%), fatigue (51.3%), and vomiting (48.7%). Other clinically significant NKTR-102-related TEAEs with an incidence rate > 10% included anorexia, dehydration, alopecia, electrolyte disturbances like hypokalemia and hypomagnesemia,

abdominal pain, anemia, and blurred vision, in decreasing order of frequency. Prolonged severe diarrhea with dehydration leading to pre-renal azotemia and subsequent acute renal insufficiency has been fatal in three patients in the ongoing Phase II studies in metastatic colorectal, ovarian, and breast cancers (one patient in each study). To date, early onset cholinergic diarrhea (as seen with irinotecan) has not been observed in any patient who received NKTR-102. Given the extended $t_{1/2}$ of SN38 derived from NKTR-102 (approximately 50 days), late onset diarrhea may occur and can be life-threatening if treatment is delayed. Early, proactive, and aggressive intervention with anti-diarrheal therapy, IV hydration, and maintenance of electrolyte balance is essential to prevent volume depletion, electrolyte imbalances, and the development of kidney failure.

Myelosuppression, especially neutropenia, can occur in patients receiving NKTR-102. Neutropenia in the setting of dehydration and unresolving GI toxicities may lead to the development of life-threatening or fatal sepsis. To date across all clinical studies, three patients have died within 30 days from last dose of NKTR-102 due to potentially drug-related neutropenic sepsis or complications of neutropenic sepsis, such as septic shock.

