4 METHODOLOGY

4.1 Study Design

This is a single stage Phase II study of relapsed small cell lung cancer patients who have received only one prior systemic therapy regimen. There will be 2 patient cohorts: those progressing on first-line therapy < 3 months after completion of treatment (Group A: chemo resistant) and those progressing on first-line therapy \geq 3 months after completion of treatment (Group B: chemo sensitive). Eirinotecan pegol will be administered at 145 mg/m² IV once every 3 weeks. Cycles will be repeated every 21 days (\pm 3 days) until disease progression. Patients who develop metastases in the central nervous system (CNS) as the only site of disease progression could receive therapeutic whole brain radiation therapy (WBRT), or gamma knife radiosurgery and after completion of WBRT continue on NKTR-102. Imaging studies are scheduled to be obtained after every other 21-day cycle.

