4.2 Target Accrual and Study Duration

A maximum of 38 subjects (20 patients from Group A and 18 patients from Group B) at multiple sites, including RPCI will be enrolled. Accrual is expected to take up to 4 years. Patients will be on study for approximately 18 – 24 months.

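### The single-stage design is valid, but it omits a futility look that would fit within the same sample sizes, final cut-offs and stated error rates at a small cost in power

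*Combined protocol and SAP*

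**What the plan says.** Section 4.1 opens with "This is a single stage Phase II study of relapsed small cell lung cancer patients", and section 11.1 applies one stage to each group separately: "A single-stage design will be used to assess the primary endpoint for each patient group". The endpoint is binary: "A treatment success was defined as a patient who was progression-free at 18 weeks".

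- **Group A.** The null and target rates are set by the statement that the largest success proportion "considered ineffective in this population is 5%, and the smallest that would warrant further subsequent studies is 25" percent. On size, "Twenty evaluable patients will be entered on this study". On the decision, "If 3 or more successes are observed, this will be considered evidence that this treatment may be recommended for further testing".
- **Group B.** The null is 10%, the target 35%, the size 18, and the regimen goes forward on 4 or more successes.

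For both groups section 11.1 claims type I error below 10% and 90% power. The Group B power sentence, however, names a 25% rate, not that group's 35%.

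No futility criterion appears anywhere, and no reason is given for preferring one stage. Section 10 provides only for review at scheduled data and safety monitoring committee meetings. The synopsis expects accrual of 38 patients in about 3 years; in section 4.2, "Accrual is expected to take up to 4 years". Section 1.5 reports that prolonged severe diarrhea with its renal consequences "has been fatal in three patients in the ongoing Phase II studies", and that three patients died of potentially drug-related neutropenic sepsis or its complications.

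**The concern.** As written, a group with no success in its first 13 patients still fills. The drug carries real toxicity, second-line patients have limited survival, and accrual is slow enough for early outcomes to be known while much of a group is still to be enrolled. The plan takes inactivity seriously enough to set an ineffective rate for each group, yet it acts on that rate only at full enrolment.

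The question is whether a look could be added without more patients and without breaking the stated error rates, and how many patients it would spare.

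**Working it through.** **Inputs (section 11.1).** A: p0 = 0.05, p1 = 0.25, n = 20, success at 3 or more. B: p0 = 0.10, p1 = 0.35, n = 18, success at 4 or more. All probabilities are exact binomial.

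**1. The plan's own design.**
- A: P(X ≥ 3 | 20, 0.05) = 0.0755; P(X ≥ 3 | 20, 0.25) = 0.9087.
- B: P(X ≥ 4 | 18, 0.10) = 0.0982; P(X ≥ 4 | 18, 0.35) = 0.9217.

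These agree with the claims of type I error below 10% and 90% power at each group's target. The sizes are also the smallest single-stage sizes that meet both conditions: 19 in A gives power 0.889, and 17 in B gives 0.897. At the 25% printed for Group B, power is 0.694.

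**2. Add a futility look.** Stop if X1 ≤ r1 among the first n1; otherwise continue to the same n and the same cut-off c:

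P(success) = Σ over x > r1 of P(X1 = x) · P(X2 ≥ c − x), where X2 is binomial on n − n1 patients.

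| | A: n1 = 13, r1 = 0 | B: n1 = 12, r1 = 1 |
|---|---|---|
| Type I error | 0.0736 | 0.0919 |
| Power at group target | 0.9030 | 0.9081 |
| Early stop at null | 0.95^13 = 0.513 | 0.9^12 + 12 · 0.1 · 0.9^11 = 0.659 |
| Early stop at target | 0.75^13 = 0.024 | 0.65^12 + 12 · 0.35 · 0.65^11 = 0.042 |

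The power loss can be checked directly as the chance of being stopped at the look when the full sample would have passed:
- A: 0.0238 · P(X ≥ 3 | 7, 0.25) = 0.0238 · 0.2436 = 0.006.
- B: 0.0057 · P(X ≥ 4 | 6, 0.35) + 0.0368 · P(X ≥ 3 | 6, 0.35) = 0.0057 · 0.1174 + 0.0368 · 0.3529 = 0.014.

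At the printed 25%, Group B power with the look is 0.672.

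**3. Room for choice.** With these boundaries, 13 and 12 are the earliest looks that keep 90% power: 12 in A gives 0.8986 and 11 in B gives 0.8957. Higher boundaries at the same looks fail: 1 or fewer of 13 in A gives 0.846, and 2 or fewer of 12 in B gives 0.834. A look at 14 in A keeps power (0.906), but the early-stop probability at the null falls to 0.488.

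**4. Patients spared.** Assumption: each group accrues uniformly over the whole accrual period, with no pause during the 18-week wait.

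Overrun = 18 · n / (52 · years).
- A: 18 · 20 / 156 = 2.3 (3 years); 18 · 20 / 208 = 1.7 (4 years). A stop spares 7 − 2.3 = 4.7 to 7 − 1.7 = 5.3.
- B: 18 · 18 / 156 = 2.1; 18 · 18 / 208 = 1.6. A stop spares 6 − 2.1 = 3.9 to 6 − 1.6 = 4.4.

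Expected saving if the drug is inactive in both groups:
- 3 years: 0.513 · 4.7 + 0.659 · 3.9 = 5.0.
- 4 years: 0.513 · 5.3 + 0.659 · 4.4 = 5.6.

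The documents give total durations, not group rates, so faster filling must be shown:
- 18 months per group: overrun 4.6 (A) and 4.2 (B); saving 0.513 · 2.4 + 0.659 · 1.8 = about 2.5.
- 12 months per group: overrun 6.9 and 6.2, which uses up almost all the remaining 7 and 6; saving close to zero.

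**The case against.** The strongest reply is that this is a choice between two sound designs. One stage is declared consistently, its sizes are minimal for the stated rates, and no conclusion drawn under it would be invalid. That stands: a reader might infer that the plan's error rates are wrong or that the trial is flawed without a look, and the documents do not support that.

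A reader might also infer that the single stage buys nothing. It does keep 0.6 (A) and 1.4 (B) points of power, and filling both groups secures more data on response, duration, survival and toxicity, plus the 38 samples named in section 1.4.1. These gains are small, but they are not zero.

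Nor should the look be credited with sparing 9 patients outright. The figures of about 5 and 4 apply only when a group stops. Both groups stop with probability 0.513 · 0.659 = 0.34 under the null, and in Group A an early stop is little better than a coin toss.

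The safety argument also has limits. Section 1.3.2 places two of the three diarrhea deaths on the 14-day schedule, not the 21-day schedule used here. A count of progression-free patients does not monitor toxicity, and patients generally leave treatment at progression in any case.

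Finally, section 10 gives no meeting dates and no efficacy remit, so a look may not fall at a convenient meeting, and delay erodes the saving. These points reduce the size of the benefit. None shows that the look breaks the stated error rates, and none supplies a reason in the plan for omitting it.

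**Conclusion.** The point holds as a cheap improvement, not as a correction of an error. A futility look at 13 (A) and 12 (B) keeps both sample sizes, both final cut-offs, type I error below 10% and power above 90%. Type I error falls slightly in each group.

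Two assumptions carry the conclusion. The first is that Group B is designed for 35%. At the printed 25% neither version approaches 90% power, so that sentence is a separate inconsistency and not an argument against the look. The second is slow, even accrual, on which the size of the saving depends. Group A also has little slack, because 13 is the only look time that both keeps 90% power and stops an inactive drug more often than not.

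**What to change.** 1. In 11.1, first reconcile the Group B power sentence with that group's 35% target.
2. In 11.1, 4.1 and the synopsis, replace the single stage with a futility-only look. Group A closes to enrolment if none of the first 13 evaluable patients is progression-free at 18 weeks; otherwise it continues to 20 under the 3-of-20 rule. Group B closes if 1 or fewer of the first 12 are; otherwise it continues to 18 under the 4-of-18 rule.
3. Let accrual continue while the look matures. Define the first 13 and 12 by registration order among evaluable patients, so that replacements do not shift the look.
4. State the exact operating characteristics tabulated above, including the early-stop probabilities at null and target.
5. In section 10, say who receives the count and when.

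The cost is amendment wording, one outcome count per group, the 0.6 and 1.4 points of power, and fewer patients for secondary and pharmacogenetic work in a group that stops. No extra patients are needed. If the sponsor expects fast accrual or values the full sample more, a sentence in 11.1 giving that reason would be an acceptable alternative.

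### Group B's stated 90% power at a 25% 18-week PFS rate is wrong: the 4-of-18 rule has 69% power at 25% and reaches 92% only at the 35% target

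*Combined protocol and SAP*

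**What the plan says.** All of this is in section 11.1, Sample Size Determination and Analysis. The two cohorts are tested separately: "A single-stage design will be used to assess the primary endpoint for each patient group". The endpoint is binary: "A treatment success was defined as a patient who was progression-free at 18 weeks". The number of successes is taken to be binomial.

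For Group B, the rate regarded as "ineffective in this population is 10%, and the smallest that would warrant further subsequent studies is 35" percent. The size and lower half of the decision rule follow: "Eighteen evaluable patients will be entered on this study. If 3 or fewer successes are observed, this regimen will be considered ineffective". Four or more successes count as support for further testing.

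The Group B description closes with a Type I error below 10% "and has 90% power to detect 25% 18-week PFS rate. Patients who come off study". The final words of that quote belong to the next sentence, on patients who leave the study early. The same Type I error and power statement appears, word for word, at the end of the Group A description. There the rates are 5% and 25%, with 20 patients and success at 3 or more.

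The synopsis and section 4.2 give sample sizes but no power, so nothing elsewhere corrects the Group B figure.

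**The concern.** The paragraph attaches two different alternatives to Group B. The hypotheses set 35% as the smallest rate worth pursuing; the power sentence refers to 25%. Both cannot be the rate at which 18 patients give 90% power.

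This is the only power figure given for the primary endpoint in one of two separately tested cohorts (18 of 38 patients), and the rule it describes ends in a go/no-go statement. Someone relying on the sentence would read 3 or fewer successes as good evidence against a 25% rate, with a one-in-ten chance of having missed it. If the power at 25% is much lower, that reading is unsafe, and a final report that copies the sentence would carry the wrong design alternative.

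**Working it through.** **Inputs (all from section 11.1)**

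| | Group A | Group B |
|---|---|---|
| Ineffective rate p0 | 5% | 10% |
| Target rate p1 | 25% | 35% |
| Evaluable patients n | 20 | 18 |
| Success if X ≥ r | 3 | 4 |
| Rate named in the power sentence | 25% | 25% |

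**Formula.** With X binomial(n, p), the probability of declaring success is P(X ≥ r) = 1 − Σ C(n,k) p^k (1−p)^(n−k), summed over k = 0 to r−1. At p0 this is the Type I error; at an alternative rate it is the power.

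**Group A, as a check on the method**
- At 5%: 1 − (0.3585 + 0.3774 + 0.1887) = 0.0755, below 10% as stated.
- At 25%: 1 − (0.0032 + 0.0211 + 0.0669) = 0.909, which agrees with the stated 90%.

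The plan's Group A figures reproduce, so the exact binomial is the right reading of the text.

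**Group B, same calculation** (terms for k = 0, 1, 2, 3)
- At 10%: 1 − (0.1501 + 0.3002 + 0.2835 + 0.1680) = 0.098. The Type I error claim holds.
- At 25%, the rate in the sentence: 1 − (0.0056 + 0.0338 + 0.0958 + 0.1704) = 0.694. The stated 90% does not reproduce.
- At 35%, Group B's own target: 1 − (0.0004 + 0.0042 + 0.0190 + 0.0547) = 0.922.

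Solving P(X ≥ 4 | 18, p) = 0.90 gives p = 33.4%, the smallest true rate that this rule detects with 90% power.

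**Could another reading rescue 90% at 25%?**
- A lower cut-off: 3 of 18 gives power 0.865 but Type I error 0.266; 2 of 18 gives 0.961 but 0.550.
- Normal approximation to the 4-of-18 rule: 0.607, or 0.707 with continuity correction.
- One-sample normal-approximation power with n = 18: 0.720 at one-sided 10%, and 0.629 at one-sided 5% or two-sided 10%.

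None gives 90% power at 25% with Type I error below 10%.

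**Where the 25% came from.** Searching single-stage designs for Type I error below 10% and power of at least 90%, the smallest for 10% against 35% is exactly n = 18 with success at 4. The smallest for 5% against 25% is exactly n = 20 with success at 3. Both cohorts were therefore evidently built on their stated targets, and Group B's sentence took Group A's rate. For scale only, the smallest design for 10% against 25% is n = 40 with success at 7 (Type I error 0.0995, power 0.904).

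**The case against.** The strongest reply is that the design is not at fault. Group B's hypotheses are stated correctly a few sentences before, and at the declared 35% target the rule misses only 1 − 0.922 = 7.8% of the time, inside the promised 10%. On the plan's own terms a 25% rate in Group B falls between the null and the target, so the trial never undertook to detect it. The 30.6% miss rate misleads only someone who reads the power sentence without the 35%. The decision depends on the success count alone, so no analysis or conduct changes. Changing one number, 25% to 35%, would be a complete correction.

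Most of this stands. The sample size, cut-off and Type I error need no change; the 40-patient figure is illustrative and does not mean the cohort is too small; and the one-number change would make the sentence true. What does not follow is that the error can be left. The sentence is a plain numerical claim about the primary analysis, it is about 21 percentage points out (90 − 69.4), and it contradicts the target in its own paragraph.

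**Conclusion.** The concern holds. The figure to correct is the alternative rate attached to Group B's power: the 90% claim is true at 35% (92.2%) and false at 25% (69.4%). The chance of wrongly dismissing a true 25% rate is 30.6%, about three times the 10% that the text implies. The result rests on the plan's own assumptions: independent binomial outcomes, exactly 18 evaluable patients, and success at 4 or more. It needs no outside figure. It must be fixed because it misstates the operating characteristic of the primary endpoint in one of the two cohorts, although the Group B design itself is adequate for 10% against 35%.

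**What to change.** In section 11.1, replace the Group B power sentence with wording such as:

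> Under the binomial model, this design has a Type I error of 9.8% at a true rate of 10% and 92% power to detect a 35% 18-week PFS rate (69% power at 25%).

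The minimum correction is to change 25% to 35%. Giving the 25% figure as well is optional, but it tells the reader what a negative result can and cannot exclude. Keep n = 18, the 4-success rule and the Group A text. The cost is one sentence in the protocol, with no extra patients and no change to the analysis.

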	
≤ 14 days prior to initiation of study drug, Cycle 1 (Day 1 and weekly), and prior to treatment on Day 1 of subsequent cycles, 30-Day Follow-Up.
 
Performance Status: ≤ 14 days prior to initiation of study drug, Cycle 1 (Day 1 and weekly), and prior to treatment on Day 1 of subsequent cycles, 30-Day Follow-Up.
 
12-Lead ECG: ≤ 14 days prior to initiation of study drug and prior to treatment on Day 1 of Cycle 2 and Cycle 3, if clinically indicated.

Statistical Analysis
	
Efficacy Assessments:
 
 • 18-week PFS is defined as the proportion of patients whose disease has not progressed at 18 weeks after getting etirinotecan pegol. • Tumor response is defined as a complete response (CR) or partial response (PR) by RECIST 1.1 criteria, which will be evaluated by CT-scan every other cycle. • OS is defined as the time from enrollment to death from any cause. 
Safety Assessments:
 
 • The maximum grade for each type of adverse events (AEs) will be recorded for each patient based on NCI CTCAE version 4.0, and frequency tables will be reviewed to determine AE and toxicity (unrelated, unlikely, possible, probably, or definitely related to study treatment) patterns in each group. • A single-stage design will be used to assess the primary endpoint separately for each. Based on this, the primary endpoint of this trial will be the proportion of patients who are progression-free at 18 weeks.

Study Schema

INVESTIGATOR STUDY ELIGIBILITY VERIFICATION FORM

Subject Name: (Network sites use subject initials): _____

Medical Record No.: (Network sites use subject ID): _____

Title: A Phase II Study of Single Agent Topoisomerase-I Inhibitor Polymer Conjugate, Etirinotecan Pegol (NKTR-102), in Patients with Relapsed Small Cell Lung Cancer

INCLUSION CRITERIA				
Yes	No	N/A	All answers must be "YES or "N/A" for patient enrollment.	Date
			1. Written informed consent granted prior to initiation of any study-specific screening procedures, given with the understanding that the patient has the right to withdraw from the study at any time, without prejudice.	
			2. 18 years of age or older.	

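### Off-protocol therapy before week 18 is a failure in the primary endpoint but not an event in the PFS curve, so the Kaplan–Meier estimates can run above the primary proportion

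*Combined protocol and SAP*

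**What the plan says.** Section 11.1 sets up the primary endpoint as a count: "A treatment success was defined as a patient who was progression-free at 18 weeks". The decision rules use that count: 3 or more successes of 20 in Group A, 4 or more of 18 in Group B. The same paragraph adds that patients who come off study, with toxicity as the example, and "start an off-protocol therapy prior to 18 weeks will be considered failures at that point".

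The time-to-event analysis follows. "Progression-free survival is defined as the time from registration to the date of first documented disease progression or death". On censoring there is one sentence: "Patients who loss-to-follow-up or alive at time of analysis will be censored at the last contact of known alive". The method is Kaplan–Meier: "The distribution of time to disease progression and survival time will be estimated in each group using the method of Kaplan–Meier". The outputs include an 18-week figure: "Probability of PFS at 18 weeks and 24 week and probability of survival at 3, 6, and 9 months will be estimated".

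The synopsis (Statistical Analysis) has its own wording: "18-week PFS is defined as the proportion of patients whose disease has not progressed at 18 weeks after getting etirinotecan pegol". It does not mention off-protocol therapy.

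After treatment stops, Table 4 shows no tumor assessment at the 30-day visit or in survival follow-up. Section 7.13 provides for survival contacts every 3 months, which may be by telephone. Section 7.5 refers to end-of-treatment evaluations without listing them.

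**The concern.** Consider a patient who stops for toxicity at about week 10, starts another drug, and has neither documented progression nor death by week 18. In the success count this patient is a failure. In the PFS curve, as defined, no event has occurred and the patient stays at risk until last known alive. Since no scan is scheduled after treatment stops, survival contact alone can carry the patient as progression-free through week 18, and the time on the next drug is credited to NKTR-102.

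Such patients are plausible. Section 1.3.2 gives a median onset of Grade 3 diarrhea on the 21-day schedule of 93 days (range 8 to 107), inside the 126 days that make up 18 weeks. Section 7.2 requires discontinuation for several toxicities.

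At stake is a published Kaplan–Meier 18-week PFS that is higher than the primary proportion for the same patients, under nearly the same name, with nothing in the plan to explain the gap. The 24-week estimate is affected in the same way.

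**Working it through.** **1. The plan's own figures.** Group A has n = 20, success at 3 or more, and rates of 5% and 25% (the rate that "would be considered ineffective in this population is 5%, and the smallest that would warrant further subsequent studies is 25"%). The exact binomial gives type I error P(X ≥ 3 | 0.05) = 0.0755 and power P(X ≥ 3 | 0.25) = 0.909, which reproduces the stated below-10% error and 90% power. Group B has n = 18, success at 4 or more, and rates of 10% and 35%, giving 0.0982 and 0.922. (The Group B power sentence prints 25% as the alternative; that is a separate matter.) These properties belong to the success count. No threshold is attached to the Kaplan–Meier estimate.

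**2. Notation.** S = successes; O = patients who start off-protocol therapy before week 18 with no documented progression or death by then; E = n − S − O = events before week 18. The documents give no value for O. I assume 0 to 4 patients per group, with no other censoring before week 18, and I ignore the small difference between counting from registration and from first dose.

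**3. Formulas for the 18-week figure.**
- Primary proportion: S/n.
- Kaplan–Meier, switchers at risk past week 18 (last contact alive is later): (S + O)/n.
- Kaplan–Meier, switchers censored before all events: S/(n − O).
- Kaplan–Meier, switchers censored after h of the E events: [(n − h)/n] × [S/(n − h − O)].

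**4. Group A, S = 2, O = 3, E = 15.**
- Primary: 2/20 = 10%.
- At risk past week 18: 5/20 = 25%.
- Censored before all events: 2/17 = 11.8%.
- Censored midway (h = 7): (13/20) × (2/10) = 13.0%.
- Censored at a switch that comes after all 15 events: 5/20 = 25% again, so the gain from censoring depends on how early the switches fall.

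**5. Range over the assumed number of switchers.**

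| Group | O | Primary | At risk past week 18 | Censored before all events | Censored midway |
|---|---|---|---|---|---|
| A (S = 2) | 0 | 10% | 10% | 10% | 10% |
| A | 1 | 10% | 15% | 10.5% | 10.9% |
| A | 2 | 10% | 20% | 11.1% | 12.0% |
| A | 3 | 10% | 25% | 11.8% | 13.0% |
| A | 4 | 10% | 30% | 12.5% | 14.4% |
| B (S = 3) | 0 | 16.7% | 16.7% | 16.7% | 16.7% |
| B | 1 | 16.7% | 22.2% | 17.6% | 18.3% |
| B | 2 | 16.7% | 27.8% | 18.8% | 20.0% |
| B | 3 | 16.7% | 33.3% | 20.0% | 22.2% |
| B | 4 | 16.7% | 38.9% | 21.4% | 24.1% |

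Each switcher kept at risk adds 1/20 = 5 points in Group A and 1/18 = 5.6 points in Group B.

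**6. Which column does the plan imply?** Suppose the last dose is on day 63 (after three 21-day cycles). The 30-day visit falls near day 93, and the first survival contact about 91 days later, near day 184. A patient reached then is last known alive after day 126, so the censoring rule as written gives the third numeric column.

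**7. After the fix.** With switches counted as events, Group A has 15 + 3 = 18 events and Kaplan–Meier gives 2/20 = 10%, equal to the primary proportion.

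**The case against.** Several points on the other side stand.

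- **No second decision rule.** A reader might infer that the trial could reach opposite conclusions. The documents do not support this: only the success count has a cut-off, and 25% is the Group A design alternative, not a Kaplan–Meier criterion.
- **The primary figure is already named.** Section 11.1 and the synopsis both make the proportion the 18-week measure.
- **The gap is conditional.** A reader might infer that the two rates will differ. They agree if nobody switches before documented progression and nobody is censored before week 18, and no switching rate is given.
- **The censoring sentence may be meant for survival.** It follows the survival-time definition and fits PFS poorly. If switchers were instead censored when they switch, the gap could be much smaller. But no other rule is written for PFS.
- **Some switchers are already events.** Section 7.3.5 treats a need for radiation as progression (with a CNS-only exception in Section 7.4), and Section 8.4 counts symptomatic deterioration as progressive disease. Section 8.4 excludes deterioration related to study treatment, so a patient who stops for toxicity is not caught.
- **Dating the failure may signal intent.** Placing the failure at the time of the switch could mean it was to carry into the curve. The PFS definition does not say so.
- **Progression-or-death PFS is a legitimate descriptive measure.** It is, but it then needs its own label and a censoring date tied to tumor assessment.

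**Conclusion.** The mismatch is explicit, but its consequence is limited to reporting. The go/no-go decision and its error rates are untouched. The Kaplan–Meier 18-week PFS can exceed the primary proportion, and the 24-week estimate has the same upward bias.

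With 2 successes in Group A and an assumed 3 switchers, the primary is 10% and Kaplan–Meier is 25% under the censoring rule as written. It is 11.8% to 13.0% if the switchers are censored at a switch before or midway through the other events. The 25% is the top of that range and should not be quoted alone. With no switchers and no early censoring the difference is zero.

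The direction is one-way, provided patients of unknown status are not counted as successes. The size rests on the assumed number of switchers and on when they are censored; the documents fix neither in advance. Because the remedy is cheap and removes a choice between two figures after the data are seen, it should be made.

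**What to change.** In the PFS paragraph of Section 11.1:

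1. For the PFS curve and its 18- and 24-week probabilities, count the start of off-protocol anticancer therapy as an event on its start date. Up to week 18 this is the plan's own failure rule; for starts between weeks 18 and 24 it extends that rule.
2. Report the curve with only progression or death as events as a labelled sensitivity analysis, censored at the last tumor assessment rather than at last contact alive. Keep last contact alive as the censoring rule for overall survival.
3. State that the binomial proportion remains the figure for the decision, and that the Kaplan–Meier estimates are descriptive.

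The cost is a few sentences, one extra curve, and a Kaplan–Meier figure that may be slightly less favourable. No dose, visit, sample size or decision rule changes.
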